## Potential Risks

One potential risk is overheating the moldable material when fitting. The device is placed in boiling water to make it pliable and then molded to the individual user. These 'boil and bite' mouthguards have been on the market for more than 40 years, and this device has no higher risk than these OTC products currently on the market. The product instructions are clear about instructing patients to ensure that the mouthpiece is at a suitable temperature prior to application.

A silicon strap on the device keeps the tongue from falling back, preserving the airway. It might be possible for this strap to break free and be swallowed. This is an unlikely risk, as it is held in place by two different attachment points, so even if one side of the strap were to break free, there would no longer be any stress on the other side of the strap, which makes it highly unlikely that both sides of the strap would break at the same time. During the 510k approval process for the Zyppah Boil and Bite, the FDA was presented with data showing the forces necessary to break the silicon strap. With more than 100,000 users of the product per year, there has not been a single reported or known incident where both sides of the strap have come off. However, even if the silicon strap were to break free, the silicon is inert and should not cause any health concerns if swallowed.

The device does not advance or adjust the position of the jaw, so there is no risk of TMJ issues or bite changes. The top and bottom halves of the device are locked together, preventing any jaw advancement.

One potential concern is the ability of the mouthpiece to pull out fillings or crowns. However, the device is made of a soft material with limited retentive abilities. With more than 100,000 users of the product, no known incidence of a filling, crown, or tooth being pulled out by the device has been reported. In addition, the device is made of the same material used safely for more than 40 years with mouthguards and other intraoral devices.

Mouth or tooth soreness can also result from the use of any intraoral device. If a patient experiences any significant soreness, it is likely the result of an improper molding of the device to the teeth. The device can be re-molded up to three times to make sure a correct fit is generated. If the patient is unable to generate a correct fit and the tooth soreness persists, they are instructed to contact customer service and discontinue use. This risk is identical to that of other OTC mouthguards.

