#### Study Design

Patients will enroll in the study online. The on-line experience has been carefully designed to mimic the experience of buying the device in a retail store or on a website without consulting a sleep professional or dentist. After filling out a short online questionnaire to determine their initial symptoms and signing the informed consent, the product and instructions will be shipped to them. The device is used for a period of 10 days in the clinical trial. An email prompting them to complete a follow-up questionnaire will be sent ten days after the device has been received. Upon completion of the follow-up survey, the cost of the device will be refunded to the patient, incentivizing completion of the study.

The surveys will ask the patients to qualitatively and quantitatively compare their snoring before use of the device and after 10 days of using the device.

As part of the follow-up survey, users will be asked if they self-identified (on the basis of the product instructions) as being at risk for OSA. If they answer positively, they will be asked about their response, including whether they sought medical care, enrolled in a sleep study, or discontinued use of the device.

A two-sample t-test will be used to analyze the change from the initial survey to the follow-up survey, with patients serving as their own controls.

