## Methods and Procedures

## Methods and Procedures

Subjects who are interested in reducing their snoring will be recruited online. In order to participate in the trial, they will complete a pre-trial questionnaire, as well as review and sign the Informed Consent.

Assuming they satisfy the Inclusion and Exclusion criteria and sign the Informed Consent (includes the inclusion/exclusion criteria), they will purchase the device for \$90. The intraoral device and patient instructions will be mailed to them (Attachment E).

Once the subject is able to participate in the study, the device is placed in boiling water to soften it. While still warm, the device is placed in the mouth and molded to the individual patient. This is the same procedure used with many intraoral mouthpieces and devices including the Zyppah Boil and Bite.

The subject will be asked to use the intraoral device each night for ten consecutive nights. After they have used the device for ten days, a follow-up survey will be emailed to the subject. The patient will respond to the questions in the survey. After they have completed the follow-up survey and returned it, the subject will receive a full refund for the cost of the device (\$90). This is intended to increase compliance with the protocol.

This study will also evaluate the response of subjects who are at high risk of obstructive sleep apnea. The product instructions will contain a brief questionnaire (Attachment D, STOP-BANG Survey) assessing the subject's risk for OSA. If they are determined to be high-risk by the self-administered questionnaire, they will be given the following options: 1) complete a full, overnight in-office sleep study, 2) complete a discounted in-home sleep study, or 3) discontinue use of the device and return it for a full refund. The response of these subjects will be monitored to see how they respond and whether they continue to use the device or seek medical attention to evaluate their risk of sleep apnea.

This is a non-significant risk study, and the only 'extra' requirements for this study are the completion of the pre-study and post-study questionnaires by the patient.

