# Data Analysis and Monitoring

The primary endpoints, a VAS assessment of snoring and the Snoring Severity Scale will be analyzed using a two-sample *t*-test comparing the pre-study and post-study questionnaire results. The ANCOVA method may also be used to evaluate the impact of different variables, like age, weight, gender, or others, on the study results. There are no potential serious risks to patients, and no stopping criteria that need to be analyzed during the study.

In determining sample size, it was estimated that the device would produce a 15% improvement in snoring, as measured on the VAS. With a level of significance of p < 0.05 and a power of 80%, approximately 350 subjects will need to complete the study to generate statistically significant data. Assuming a 30% dropout rate for non-compliance with the study or the discovery of moderate to severe sleep apnea, 500 subjects will be enrolled in the study to ensure the study is adequately powered.

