## Transition from Research Participation

As this research study only asks patients to use the product as they would normally, subjects will continue with their use according to the device instructions, and are free to stop use at any time following the post-study survey after 10 days of application.

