## Costs to the Subject

The subject will not incur any costs as the result of participating in the study. The subject will pay for the device upon enrollment, at a cost of \$90, which will be refunded immediately after the completion of the follow-up survey. Should the subject not complete the follow-up, the cost of the device would not be refunded, encouraging compliance with the study protocol. Should the subject have any costs related to complications of the device, that are not covered by insurance, they will be paid by the Sponsor.

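### The protocol gives two conflicting triggers for the only outcome survey, and under the use-based trigger subjects who stop the device early have no assured primary outcome

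*Combined protocol and SAP*

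**What the plan says.** The post-study survey is the only source of follow-up data for both primary endpoints, the VAS and the Snoring Severity Scale (SSS). The protocol gives two rules for when it goes out:

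- Study Design: "An email prompting them to complete a follow-up questionnaire will be sent ten days after the device has been received". Continued use is not a condition.
- Methods and Procedures: "After they have used the device for ten days, a follow-up survey will be emailed to the subject". Use is the condition.

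On early stopping, Potential Risks deals with subjects who cannot obtain a fit and remain sore: "they are instructed to contact customer service and discontinue use". Risk Category also allows use to end at once if complications occur. Transition from Research Participation, by contrast, says that subjects "are free to stop use at any time following the post-study survey after 10 days of application".

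Data Collection lists the post-questionnaire as Attachments B (VAS), C (SSS) and D (STOP-BANG). Study Design adds questions for subjects who identify themselves as at risk of obstructive sleep apnea (OSA), including "whether they sought medical care, enrolled in a sleep study, or discontinued use of the device".

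The sample size in Data Analysis and Monitoring rests on about 350 completers out of 500 enrolled: "Assuming a 30% dropout rate for non-compliance with the study or the discovery of moderate to severe sleep apnea". Subject Selection describes the same 30% as drop-out or unreturned questionnaires. Neither Data Analysis and Monitoring nor Statistical Analysis names an analysis set or a rule for missing outcomes.

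**The concern.** There is no control group, so selective loss before the follow-up survey goes straight into the estimate. A subject who stops because the device hurts or will not fit is plausibly one who gained little from it. If such subjects are not surveyed, the primary comparison is made mainly in people who tolerated the device for ten days, while the question for an over-the-counter product concerns everyone who receives it.

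The same loss affects tolerability, which matters because the study's stated purpose covers safety as well as efficacy. Early stoppers are the most informative subjects on this. The protocol describes no route from customer service to the study coordinator, who alone holds the data under Data Storage and Confidentiality.

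**Working it through.** **1. The plan's own figure.** Inputs from Data Analysis and Monitoring: about 350 completers and 30% drop-out. 350 / (1 − 0.30) = 500, which reproduces the planned enrolment. The plan therefore allows for 500 − 350 = 150 subjects without a primary outcome.

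**2. One subject under each trigger.** Take a subject who cannot get a fit, stays sore and stops on night 3.

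- *Study Design rule (time since receipt).* The email arrives as scheduled. The subject can give VAS and SSS answers and obtain the refund.
- *Methods and Procedures rule (ten days of use).* The condition is never met, so no email is assured, and neither is a VAS or SSS result.

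Whether this subject has an outcome depends entirely on which section is followed.

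**3. What a returned survey would show.** Even if the survey is sent, Attachments B, C and D are not described as recording whether, when or why use stopped. The discontinuation question is put only to those who see themselves as at risk of OSA. For other respondents, an answer given off the device could not be told apart from one given on it.

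**4. Illustrative size.** Let *m* be the share unassessed and *c* their mean change. Assume that completers improve by the planned 15% on the VAS.

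Effect in all recipients = (1 − m) × 15% + m × c

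With c = 0:

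- m = 0%: 15%
- m = 10%: 0.90 × 15% = 13.5%; the completer figure is 15 / 13.5 = 1.11 times as large
- m = 20%: 0.80 × 15% = 12.0%
- m = 30%: 0.70 × 15% = 10.5%; 15 / 10.5 = 1.43 times as large

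At m = 30% with other values of c:

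- c = −5%: 10.5% − 1.5% = 9.0%
- c = +7.5%: 10.5% + 2.25% = 12.75%

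The documents give neither *m* for early stoppers nor *c*; all these values are assumptions. Within the plan's allowance, 30% is an upper bound, because it also covers discovered sleep apnea and unreturned questionnaires.

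**5. Can the study carry a no-change sensitivity analysis?** The plan gives no SD, so this needs a further assumption. Reading the 15% as a standardised paired effect of 0.15 gives n = ((1.960 + 0.842) / 0.15)², about 349, close to the plan's 350. Now analyse all 500, with 30% set to exactly zero change:

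- mean = 0.70 × 0.15 = 0.105
- variance = 0.70 + 0.30 × 0.70 × 0.15² = 0.7047
- z = 0.105 × √500 / √0.7047 − 1.960 = 0.84, so power is about 80%

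If those 30% instead had mean zero change but the same SD as completers, power would be about 65%.

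**The case against.** A reader might infer more: that early stoppers have no scheduled assessment, are written off as drop-outs, and are paid to keep using the device. The documents do not support this.

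- **Assessment.** Study Design schedules the survey by time since receipt, whatever the use. The gap arises only under the wording in Methods and Procedures.
- **Drop-out status.** The only subjects expressly dropped are the at-risk users in the OSA section who seek a sleep study or return the device for a refund. For soreness or poor fit, it is an inference from the word non-compliance. That word may mean only an unreturned survey: Methods and Procedures names the two questionnaires as the study's only extra requirements. Stopping for lack of benefit is not addressed anywhere. The 30% is a planning allowance, not an exclusion rule.
- **Refund.** It depends on the survey: "which will be refunded immediately after the completion of the follow-up survey", and "Should the subject not complete the follow-up, the cost of the device would not be refunded, encouraging compliance with the study protocol". No section requires ten nights of use for it. Under the receipt-based trigger, the $90 gives early stoppers a reason to answer. It becomes a reason to stay on the device only if the survey itself waits for ten days of use.
- **Stopping rules.** The transition section mainly concerns use after the study and does not forbid earlier stopping. The consent form and the attachments themselves were not available for this review and may say more.

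These points stand, and they narrow the finding. They do not remove the conflict between the two triggers, the missing link from customer service, the absence of a general item on stopping, or the absence of an analysis set.

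**Conclusion.** The point holds in a limited form. Study Design and Methods and Procedures conflict on what triggers the only outcome survey. If Methods and Procedures is followed as written, early stoppers have no assured VAS or SSS result and the completers' mean change would tend to overstate the effect in all recipients. If Study Design is followed, the assessment exists, but for most respondents nothing is described that shows whether the device was still in use.

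The direction rests on the assumption that unassessed subjects do less well than completers. The size cannot be estimated from the documents. The range of 15% down to 10.5% is an illustration that assumes 15% in completers, no change in the unassessed, and 0% to 30% unassessed. If stoppers answer the receipt-based survey, the loss could be close to nil. The matter should be settled before data collection, because stopping dates and reasons cannot be reliably recovered afterwards.

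**What to change.** - **Methods and Procedures:** adopt the fixed time after receipt already in Study Design, and send the survey to every subject shipped a device, whether or not it is still used.
- **Data Collection:** add one post-questionnaire item for all subjects: still using the device and, if not, the date and reason for stopping.
- **Potential Risks:** have customer service report each early stop to the study coordinator.
- **Data Analysis and Monitoring:** define the primary analysis set as all subjects shipped a device who return a survey, and say how this fits with the at-risk users dropped under the OSA section. Add a sensitivity analysis with non-returners set to no change.
- **Transition from Research Participation, Risk Category and Potential Risks:** reconcile what these sections say about when subjects may stop. Which rule should apply is for the sponsor and the investigator.

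The refund terms need no change of substance once the trigger is fixed. The cost is protocol wording, an email setting, one survey item and one extra analysis. The reported improvement will probably be somewhat smaller.

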# Protection against Risks

To minimize the risk of contacting the mouth with a hot mold, the instructions for use have multiple bolded, red warnings about the boiling water. The risk of the silicon strap breaking free is mitigated by the design of the device, which makes it highly unlikely that it would break free of both attachment points, as well as by the inert silicon composition. The material that the device utilizes minimizes the risk of pulling out any dental fillings or crowns, and the ability to re-mold the device if there are any sore spots reduces the risk of mouth or tooth soreness. If there is any lingering mouth soreness, it should be temporary and cease when use of the device is discontinued.

# Alternatives to Participation

Participants have many other options to choose in trying to reduce or eliminate snoring. Nose strips, which attempt to increase the amount of air that can pass through the nasal passage, are available over-the-counter. Other intraoral devices designed to combat snoring are available as either over-the-counter or prescription devices. Simple lifestyle changes, including losing weight, avoiding alcohol

consumption prior to sleeping, and sleep position can also be effective for some patients with habitual snoring.

If the more serious condition of severe obstructive sleep apnea is suspected, patients are encouraged to go through a sleep study to conclusively diagnose sleep apnea. Sleep apnea can be treated with a CPAP machine, or with various other intraoral devices under the care of a sleep specialist or dentist.

# Process of Consent

Consent will be obtained through online forms. The respondent will read through and initial at the primary sections throughout the informed consent, ensuring they have reviewed the document, before providing an electronic signature after reviewing the Informed Consent in its entirety.

There will be no coercion or undue influence, as these subjects are not being reimbursed for participating in the study (other than receiving the study materials free of cost) and are free to decline to participate at any point in the enrollment process.

# Subject Capacity

All subjects will have the capacity to give informed consent.

## Subject Comprehension

Comprehension will be addressed by having the prospective subject read and initial at the conclusion of each segment of the informed consent, ensuring they have read and comprehend the material. If they do have questions about the language or meaning of the document, they will be able to contact the sponsor directly to ask any questions they might have.

## **Consent Documentation**

Consent will be required before the subject can go forward with the ordering process of the study, ensuring that no subjects will be able to enter the study or receive the product without having read and agreed to the informed consent. This will be documented and stored using the same system described in the Data Storage section.

## Costs to the Subject

The subject will not incur any costs as the result of participating in the study. The subject will pay for the device upon enrollment, at a cost of \$90, which will be refunded immediately after the completion of the follow-up survey. Should the subject not complete the follow-up, the cost of the device would not be refunded, encouraging compliance with the study protocol. Should the subject have any costs related to complications of the device, that are not covered by insurance, they will be paid by the Sponsor.

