## II. Purpose and Background

The purpose of this study is to evaluate the safety and efficacy of an over-the-counter (OTC) intraoral mouthpiece to reduce snoring. A secondary objective is to evaluate the behavior of patients at high risk for sleep apnea to determine whether they will seek a conclusive diagnosis with a sleep study.

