## Obstructive Sleep Apnea (OSA)

Obstructive Sleep Apnea (OSA) is a sleep disorder where breathing stops and restarts multiple times during the night, interrupting sleep and often abruptly awakening the patient with a feeling of suffocation. There is significant overlap between snoring and patients with obstructive sleep apnea, which is estimated to affect 3-7% of men and 2-5% of women (Punjabi NM, *The Epidemiology of Adult Obstructive Sleep Apnea*, Proceedings of American Thoracic Society, 5:2, 2008).

The vast majority of those with sleep apnea also habitually snore, though the majority of habitual snorers *do not* have sleep apnea. From prevalence estimates, approximately 10% of male and 22% of female snorers may also have OSA. Women are eight times more likely to have their OSA undiagnosed than men.

The instructions for use of the mouthpiece helps the patient assess their risk of mild, moderate or severe OSA and may encourage them to register for an inexpensive home sleep study. It is hoped that this device may help some habitual snorers identify their risk of OSA and seek treatment. This clinical trial will also monitor the behavior of these users, looking to see whether they i) seek a sleep study, ii) return the device for a refund or iii) decide to use the snoring device. In the first two cases, they will be dropped from the clinical trial.

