# Payment for Participation

No payments will be given for participation, other than providing the study device at no cost (should the subject complete the trial).

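### The plan conflicts with itself on whether a high-risk subject who seeks a sleep study still gets the follow-up survey and the $90 refund, so the secondary objective may lose the subjects it is meant to count

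*Combined protocol and SAP*

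**What the plan says.** All references are to the combined protocol and SAP.

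- **Secondary objective** (II. Purpose and Background): to "evaluate the behavior of patients at high risk for sleep apnea to determine whether they will seek a conclusive diagnosis with a sleep study".
- **Behaviors to be followed** (Obstructive Sleep Apnea (OSA)): whether these users "i) seek a sleep study, ii) return the device for a refund or iii) decide to use the snoring device". The next sentence reads "In the first two cases, they will be dropped from the clinical trial". It gives no timing and does not say whether a dropped subject is still surveyed.
- **Options offered to a high-risk subject** (Methods and Procedures): an in-office sleep study, a discounted home study, or to "discontinue use of the device and return it for a full refund". No refund is mentioned for either sleep study.
- **Where seeking is measured** (Study Design): in the follow-up survey, which asks subjects who identified themselves as at risk whether they sought care, enrolled in a sleep study or stopped using the device. Data Collection likewise says the post-study questionnaire serves to evaluate how high-risk subjects responded.
- **Refund rule** (Costs to the Subject): the subject pays $90, "which will be refunded immediately after the completion of the follow-up survey". The same section says "Should the subject not complete the follow-up, the cost of the device would not be refunded", and opens with "The subject will not incur any costs as the result of participating in the study".
- **Payment rule** (Payment for Participation): nothing is paid beyond "providing the study device at no cost (should the subject complete the trial").

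**The concern.** The subjects whom the secondary objective exists to count are also the subjects whom the plan removes. If removal means that no survey is sent, two things follow. Their sleep-study enrollment is not recorded by the instrument designed to record it. They also miss the event that triggers the refund, so they bear a cost that the plan says no subject bears.

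The refund is not a side issue. The sponsor relies on the $90 to influence behavior: Study Design and Costs to the Subject both present it as an incentive to complete the study. A sum expected to move survey completion could also affect whether a subject seeks a study or reports having done so. At stake is whether the reported seeking rate can be interpreted at all.

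**Working it through.** **1. The plan's own figures.** No figure is given for the sleep-study endpoint: no expected rate, no high-risk share and no denominator. The only related figure is enrollment in Data Analysis and Monitoring: 350 completers / (1 − 0.30) = 500, which reproduces. That 30% includes subjects lost through discovery of moderate to severe sleep apnea, so the plan places at least some of this group outside its 350 completers.

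**2. Refund status by choice, under each reading of the drop rule.**

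| Choice of a high-risk subject | If dropped subjects are not surveyed | If dropped subjects are still surveyed |
|---|---|---|
| Keeps using the device and answers the survey | $90 refunded | $90 refunded |
| Returns the device | $90 refunded through the return option | $90 refunded through the return option |
| Seeks a sleep study | No refund stated | Refunded under Costs to the Subject once the survey is completed; unclear under Payment for Participation, because a dropped subject has not plainly completed the trial |

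Seekers are the only row without an assured refund under both readings.

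**3. Timing.** Methods and Procedures puts the risk questionnaire and the options in the product instructions, which arrive with the device, and sends the survey after ten days of use. A seeker dropped early need not reach that point. Study Design instead counts ten days from receipt of the device, which such a subject would reach. Data Collection also places the risk questionnaire in the post-study survey. These statements do not settle which reading is intended.

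**4. Effect on the observed rate if seekers are missed.** Let *s* be the true share of high-risk subjects who seek a study and *q* the share of seekers who are never surveyed. Assume that every other high-risk subject responds. Then

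observed share = s(1 − q) / (1 − sq).

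| s (assumed) | q = 0 | q = 0.25 | q = 0.50 | q = 1 |
|---|---|---|---|---|
| 0.10 | 10.0% | 7.7% | 5.3% | 0% |
| 0.20 | 20.0% | 15.8% | 11.1% | 0% |
| 0.50 | 50.0% | 42.9% | 33.3% | 0% |

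For example, with s = 0.20 and q = 0.25: 0.20 × 0.75 / (1 − 0.05) = 0.15 / 0.95 = 15.8%. Both *s* and *q* are assumptions, because the documents give neither. The Study Design reading is q = 0, with no loss. The strictest reading of the drop rule is q = 1, where the survey records no seekers. If other high-risk subjects also go unsurveyed (returners fall under the same drop rule), the shortfall for q between 0 and 1 is smaller than shown.

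**5. Behavioral effect of the $90.** This cannot be computed. The documents contain nothing on how subjects respond to the refund, and the discount on the home study is not stated.

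**The case against.** A reader might infer something stronger: that seekers are dropped before the survey, that the plan therefore charges $90 for the behavior it measures, and that the seeking rate is biased downward. The documents do not support this, for four reasons.

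- No section says that dropping precedes the survey. Study Design and Data Collection point the other way, since the follow-up survey is where sleep-study enrollment is asked. On that reading seekers reach the survey and, under Costs to the Subject, the refund.
- Seeking is not the only path on which $90 can be lost. Any subject who skips the survey forfeits it, including one who keeps using the device. Nothing stops a seeker from also returning the device for the stated refund.
- Deterrence requires subjects to believe that seeking a study forfeits the money. No visible section tells them so, and the consent pages and product instructions are not available to check.
- The discounted home study pushes seeking upward, so the net direction of the incentives is unknown.

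All four points stand, and they remove any claim of demonstrated bias. They do not remove the conflict. The Study Design reading leaves unexplained what being dropped means, and it does not satisfy the payment section's condition that the trial be completed. A subject or coordinator following the drop, refund and payment rules as written could reasonably conclude that a seeker gets neither the survey nor the $90.

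**Conclusion.** The concern holds as a conflict between stated rules that bears directly on the secondary objective. The OSA, Study Design, Methods and Procedures, Costs to the Subject and Payment for Participation sections do not agree on whether a high-risk subject who seeks a sleep study is surveyed and refunded. Followed literally, the drop and refund rules can leave seekers uncounted and out of pocket, against the statement that participation costs nothing.

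The possible loss runs from none (every seeker surveyed) to total (no seeker surveyed, observed rate 0%). At an assumed true rate of 20% with a quarter of seekers missed, the observed rate is 15.8%. These figures assume full response from all other high-risk subjects. A net downward incentive effect is possible but not shown, and no size can be put on it. The primary endpoints and the enrollment of 500 do not depend on this point.

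**What to change.** Reconcile the five sections and state three things:

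1. Every enrolled high-risk subject, including one dropped for seeking a sleep study, is sent the follow-up survey.
2. That subject is refunded the $90 whether or not withdrawn. Say so in Costs to the Subject, in Payment for Participation, and beside the options in the product instructions.
3. The denominator for the secondary endpoint is all subjects who self-identified as high risk.

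While doing so, reconcile the list of behaviors in the OSA section, which includes continued use of the device, with the list of options in Methods and Procedures, which does not. Also reconcile the two statements of when the survey is sent. Which options subjects should be offered is for the sponsor to settle.

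The cost is $90 per refunded seeker, the same amount the sponsor already commits to for each subject who completes the survey, plus a few sentences of wording. The sample size does not change.
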